#### 10.121 Second Malignancy/ **Radiation Therapy**

A second malignancy is one unrelated to the treatment of a prior malignancy (and is NOT a metastasis from the initial malignancy).

Second malignancies require ONLY routine reporting.

All secondary malignancies that occur following treatment will be reported.

Three options are available to describe the event:

- Leukemia secondary to oncology chemotherapy (e.g., Acute Myelocytic Leukemia [AML])
- Myelodysplastic syndrome (MDS)
- Treatment-related secondary malignancy

Any malignancy possibly related to cancer treatment (including AML/MDS) should also be reported via the routine reporting mechanisms.

#### 10.122 Second Malignancy/ **Radiation Therapy**

A second malignancy is one unrelated to the treatment of a prior malignancy (and is NOT a metastasis from the initial malignancy). Second malignancies require ONLY routine reporting.

### 10.13 Monitoring and Auditing

The investigator will permit study-related monitoring, audits, and inspections by the IRB, the sponsor, and government regulatory agencies, of all study related documents (e.g. source documents, regulatory documents, data collection instruments, study data etc.). The investigator will ensure the capability for inspections of applicable study-related facilities (e.g. pharmacy, diagnostic laboratory, etc.). Participation as an investigator in this study implies acceptance of potential inspection by government regulatory authorities and applicable compliance offices

#### 10.131 Medical Monitoring

It is the responsibility of the Principal Investigator to oversee the safety of the study at his/her site. This safety monitoring will include careful assessment and appropriate reporting of adverse events as noted above, as well as the construction and implementation of a site data and safety-monitoring plan (see section 10.7 "Monitoring and Auditing"). Medical monitoring will include a regular assessment of the number and type of serious adverse events. "Any serious adverse events will be followed up by the sentinel event reporting procedure"

#### 10.132 Internal Data and Safety Monitoring Board

The trial will be reviewed by the Cancer Center Auditing area on a bi-annual or yearly basis dependent on random study selection to assess accrual, adverse events, and any endpoint problems. Any safety issues requiring protocol changes will be communicated through protocol amendments.

## 11.0 Treatment Evaluation

### 11.1 Measurement of Effect

Tumor response will be assessed, using contrast and non-contrast brain magnetic resonance imaging (MRI) with assessment based on the RANO criteria, until progression of disease (up to 2 years).

### 11.2 Definitions:

Response and progression will be evaluated in this study using the international criteria proposed by the Response Assessment in Neuro-Oncology (RANO) Working Group.[14]

**Note:** Lesions are either measurable or non-measurable using the criteria provided below. The term “evaluable” in reference to measurability will not be used because it does not provide additional meaning or accuracy.

#### 11.21 Measurable Disease

Defined as bi-dimensionally contrast-enhancing lesions with clearly-defined margins by MRI with two perpendicular diameters of at least 10 mm, visible on 2 or more axial slices which are preferably at most 5 mm apart with 0 mm skip.

In the event the MRI is performed with thicker slices, the size of a measurable lesion at baseline should be two times the slice thickness. In the event there are inter-slice gaps, this also needs to be considered in determining the size of measurable lesions at baseline. Measurement of tumor around a cyst or surgical cavity is problematic. In general, such lesions should be considered non-measurable unless there is a nodular component measuring at least 10 mm in diameter. The cystic or surgical cavity should not be measured in determining response. All tumor measurements must be recorded in millimeters (or decimal fractions of centimeters).

#### 11.22 Non-measurable Disease

This is defined as either uni-dimensionally measurable lesions, masses with margins not clearly defined, or lesions with maximal perpendicular diameters <10 mm.

#### 11.23 Target Lesions

All measurable lesions up to a maximum of five lesions should be identified as target lesions and recorded and measured (sum of the products of the perpendicular diameters) at baseline. Target lesions should be selected on the basis of their size (lesions with the longest diameters) and their suitability for accurate repeated measurements by imaging techniques. Occasionally, the largest lesions may not be suitable for reproducible measurements and the next largest lesions which can be measured reproducibly should be selected.

#### 11.24 Non-target Lesions

For patients with recurrent disease who have multiple lesions of which only one or two are increasing in size, the enlarging lesions should be considered the target lesions for evaluation of response. The other lesions will be considered non-target lesions and should also be recorded. Rarely, unequivocal progression of a non-target lesion requiring discontinuation of therapy, or development of a new contrast-enhancing lesion may occur even in the setting of stable disease (SD) or partial response (PR) in the target lesions. These changes would qualify as progression. Non-target lesions also include measurable lesions that exceed the maximum number of 5. Measurements of these lesions are not required but the presence or absence of each should be noted throughout follow-up.

#### 11.3 Guidelines for Evaluation of Measurable Disease

All measurements should be taken and recorded in metric notation using a ruler or calipers. Baseline evaluations should ideally be performed within 21 days before the beginning of treatment. These techniques should be performed with cuts of 4 mm or less in slice thickness contiguously. The MRIs will be evaluated both locally and centrally by a core lab.

#### 11.4 Response Criteria

##### 11.41 Evaluation of Target Lesions

###### 11.411 Complete Response (CR): Requires all of the following:

- Complete disappearance of all enhancing measurable and non-measurable disease sustained for at least 4 weeks
- No new lesions
- Stable or improved non-enhancing (T2/FLAIR) lesions
- Patients must be off corticosteroids
- Stable or improved clinically
- Patients with non-measurable disease cannot have a complete response. The best response possible is stable disease.

###### 11.412 Partial Response (PR): Requires all of the following:

- $\geq 50\%$  decrease compared to baseline in the sum of products of perpendicular diameters of all measurable enhancing lesions sustained for at least 4 weeks
- No progression of non-measurable disease
- No new lesions
- Stable or improved non-enhancing (T2/FLAIR) lesions on same or lower dose of corticosteroids compared to baseline scan
- The corticosteroid dose at the time of the scan evaluation should be no greater than the dose at time of the baseline scan
- Stable or improved clinically

11.413 Stable Disease (SD): Requires all of the following:

- Does not qualify for complete response, partial response, or progression
- Minimum 4 weeks duration
- Stable non-enhancing (T2/FLAIR) lesions on same or lower dose of corticosteroids compared to baseline scan. In the event that the corticosteroid dose has been increased, the last scan considered to show stable disease will be the scan obtained when the corticosteroid dose was equivalent to the baseline dose
- Stable clinically

11.414 Progression: Defined by any of the following:

- $\geq 25\%$  increase in the sum of products of perpendicular diameters of enhancing lesions compared to the smallest tumor measurement obtained either at baseline (if no decrease) or best response, on stable or increasing doses of corticosteroids
- Significant increase in T2/FLAIR non-enhancing lesion on stable or increasing doses of corticosteroids compared to baseline scan or best response following initiation of therapy, not due to co-morbid events (e.g. radiation therapy, demyelination, ischemic injury, infection, seizures, post-operative changes, or other treatment effects)
- Any new lesion
- Clear clinical deterioration not attributable to other causes apart from the tumor (e.g. seizures, medication side effects, complications of therapy, cerebrovascular events, infection, etc.) or changes in corticosteroid dose. The definition of clinical deterioration is left to the discretion of the investigator but it is recommended that a decrease in 20% of KPS or from any baseline to 50% or less be considered, unless attributable to co-morbid events.
- Failure to return for evaluation due to death or deteriorating condition
- Clear progression of non-measurable disease

11.415 Pseudoprogression (PsP): All of the following must be true:

- Progression of contrast enhancing lesions and or T2/FLAIR is restricted to the initial radiation therapy volume.
- There are no new enhancing lesions outside of the initial radiation therapy volume.
- Patients are stable or improved clinically.
- PsP may be diagnosed at any time during therapy (beyond the typical 12 week window defined by RANO).

## 11.416 Summary of the RANO Response Criteria Table

	CR	PR	SD	PD 	Preliminary PD/PsP 
T1-Gd +	None	≥50% decrease	<50% decrease- <25% increase	≥25% increase*	Any increase is restricted to initial RT Volume
T2/FLAIR	Stable or decrease	Stable or decrease	Stable or decrease	Increase*	Any increase is restricted to initial RT Volume
New Lesion	None	None	None	Present*	None
Corticosteroids	None	Stable or decrease	Stable or decrease	NA	Stable or decrease
Clinical Status	Stable or improved	Stable or improved	Stable or improved	Worsened*	Stable or improved
Requirement for Response	All	All	All	Any*	All

CR = complete response; PR = partial response; SD = stable disease; PD = progressive disease, PsP = Pseudoprogession

NA - Increase in corticosteroids alone will not be taken into account in determining progression in the absence of persistent clinical deterioration

1. RANO Progression occurs when any of the criteria with \* are present.
2. Confirmed PD requires all of the following If not all criteria are met then Preliminary PD
  - More than 3 months post RT
  - Radiologic progression by central review by RANO criteria
  - Clinical progression as determined by treating Oncologist
  - Cannot be considered Pseudoprogession
3. Patients with possible PsP should initially be given the Objective Status of Preliminary Progression. Once PsP or Progression is confirmed, the Objective Status can be changed accordingly. If Progressive Disease is subsequently confirmed, the Objective Status is to be recorded for the current cycle as PD (confirmed) and the back-dated date of the progressive disease (from the cycle with the initial Preliminary PD) is to be used as the date of progressive disease which is documented via the Event Monitoring Form. If progressive disease is not confirmed the Objective Status for the current cycle can be documented as SD, PR, or CR as appropriate using the baseline scan measurement as the baseline for comparison with the current measurement. The Objective Status for the cycle initially documented as Preliminary PD can be changed to PsP.

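### Sections 11.414 and 11.416 give two thresholds for progression, and 16.21 and 16.711 do not say which one is the primary endpoint event or how Preliminary PD still open at a read is scored

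*Combined protocol and SAP*

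**What the plan says.** Section 11.414 sets a one-criterion rule: "Progression: Defined by any of the following". Its list includes any new lesion. Footnote 1 of 11.416 repeats the rule ("RANO Progression occurs when any of the criteria with" an asterisk are present), and the PD column of the table asks for any starred item.

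Footnote 2 is attached to the same column: "Confirmed PD requires all of the following If not all criteria are met then Preliminary PD". Its four conditions are more than 3 months since radiotherapy, radiologic progression on central review, "Clinical progression as determined by treating Oncologist", and that the case cannot be considered pseudoprogression.

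The neighbouring Preliminary PD/PsP column describes a narrower group: "Any increase is restricted to initial RT Volume", no new lesion, and stable or improved clinical status.

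Footnote 3 says what happens next. For PD confirmed later, "the back-dated date of the progressive disease (from the cycle with the initial Preliminary PD) is to be used as the date of progressive disease". Otherwise, "If progressive disease is not confirmed the Objective Status for the current cycle can be documented as SD, PR, or CR as appropriate", and the earlier cycle can be changed to pseudoprogression (PsP).

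Section 16.21 defines success as being alive without evidence of progressive disease within 3 months of registration. Section 16.711 dates progression to its earliest documentation. Neither uses the words preliminary or confirmed, and neither refers to 11.416.

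**The concern.** The primary endpoint is a count of successes, so each patient must be classed one way or the other at the 10-patient and 20-patient reads. Where 11.414 and footnote 2 give different answers, the plan does not say which one drives that count. A patient who has progressed under 11.414 can remain at Preliminary PD under footnote 2, and no passage scores that status if it is still open at a read. In a single-arm trial of 20 patients, the scoring could then be settled after outcomes are known.

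**Working it through.** **Timing.** Section 7.53 gives 10 fractions on weekdays, so the last fraction falls 11 days (Monday start) to 13 days after the first, before any holidays. The endpoint window closes 3 months after registration. If radiotherapy starts on or after registration (assumption), footnote 2's condition of more than 3 months since radiotherapy is met at least about 11 days after the window closes. No progression can therefore be Confirmed PD inside the window. Under footnote 2 it can count only through footnote 3 back-dating.

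**What back-dating leaves open.** Take a patient with a persisting new lesion outside the radiotherapy volume whom the treating oncologist does not judge clinically progressed.

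| Rule | Status |
|---|---|
| 11.414, footnote 1 | Progression (new lesion) |
| Footnote 2 | Preliminary PD (no clinical progression) |
| Preliminary PD/PsP column | Does not fit (requires no new lesion) |
| Footnote 3, confirmed PD | Not reached while not judged clinically progressed |
| Footnote 3, SD/PR/CR | Does not fit (each column requires no new lesion) |
| Footnote 3, PsP | Does not fit (11.415 excludes new enhancing lesions outside the volume) |

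This patient has no defined final status. Section 1.3 summarises RANO as accepting new enhancement outside the 80% isodose line as progression even before 12 weeks, so footnote 2 is stricter than that summary. Preliminary PD with no later assessment also has no rule.

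**Stated design.** Inputs from 16.21 to 16.23: p0 = 0.20, p1 = 0.40; stop if 1 or fewer of 10 succeed; positive if 6 or more of 20 succeed.

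P(positive) = Σ over x = 2 to 10 of P(X1 = x) × P(X2 ≥ max(0, 6 − x)), with X1 and X2 each Bin(10, p). P(stop) = P(X1 ≤ 1).

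- p = 0.20: positive 0.1863, stop 0.3758 (stated alpha 0.186).
- p = 0.40: positive 0.8586, stop 0.0464 (stated power 85.9%).

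The stated figures reproduce.

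**Sensitivity to one patient.** At p = 0.20, the chance of passing stage 1 and finishing on exactly 5 successes, one short of the cut-off, is 0.148.

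**Illustration of lenient scoring.** Assume that Confirmed PD is the event, that the 20% null is a success rate under 11.414, and that a share u of null failures is scored as success. Then p = 0.2 + 0.8u.

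- u = 5%: p = 0.24, positive 0.328.
- u = 10%: p = 0.28, positive 0.486.

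If half of the null failures are deaths (assumption), which fail under 16.21 either way, p = 0.2 + 0.4u.

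- u = 5%: p = 0.22, positive 0.254.
- u = 10%: p = 0.24, positive 0.328.

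**Cost of strict scoring.** If a share v of true successes at 40% is unresolved at the read and counted as failure (assumption), p = 0.4(1 − v).

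| v | p | Power | Wrongful stage-1 stop |
|---|---|---|---|
| 0 | 0.40 | 0.859 | 0.046 |
| 5% | 0.38 | 0.815 | 0.060 |
| 10% | 0.36 | 0.764 | 0.076 |
| 20% | 0.32 | 0.637 | 0.121 |

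**The case against.** The footnotes use different terms, RANO progression and Confirmed PD, and can be read as two tiers: progression, then confirmation. Section 11.414 is the section that defines progression, and 16.21 and 16.711 read most naturally as first documented 11.414 progression. On that reading the patient above is a failure, and scoring a success means importing the word confirmed into 16.21. This is the better reading, but no passage states it, and footnote 3 prescribes a progression date only for PD that is later confirmed.

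The clinical-progression condition is undefined. If it means the oncologist's overall judgement that disease has progressed, some of these patients would be confirmed later and back-dated. That narrows the gap without closing it.

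A reader might infer from the timing condition that imaging progression can never count in the 3-month window. The documents do not support that: back-dating recovers PD confirmed later. A reader might also infer that the false-positive rate really is 0.328 or 0.486. That is not supported either. The affected shares are assumed, and 16.21 takes the 20% null from published median PFS without giving the progression criteria behind it. Section 1.6 places 30–40% of recurrences after reirradiation out of field, so such progression is not exotic. But the figure covers all recurrences, gives no clinical status, and concerns the reirradiation field, which may not be the volume 11.415 means.

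**Conclusion.** The point holds as an endpoint-definition defect and should be fixed. One PD column carries two thresholds, the endpoint sections do not choose between them, and at least two kinds of Preliminary PD have no final scoring. The design arithmetic is sound.

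The defect matters because of the small cut-offs: one ambiguous patient can turn 5 of 20 into 6, or 1 of 10 into 2. The number of such patients cannot be derived from the documents. The move from 0.186 to 0.328 is therefore an illustration that depends on Confirmed PD being the event, a 5% share, and a null rate defined under 11.414. It is not an estimate of this trial's error rate.

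**What to change.** For endpoint scoring only:

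- Reconcile footnote 2 of 11.416 with 11.414.
- State in 16.21 and 16.711 that the event is progression meeting 11.414 within 3 months of registration, dated to first documentation, unless reclassified as PsP under 11.415 and footnote 3. Radiologic and clinical progression need not both be present.
- State that Preliminary PD meeting 11.414 and unresolved at the 10-patient or 20-patient read counts as a failure. Report a sensitivity analysis scoring it as a success.
- State which radiotherapy course the initial radiation therapy volume in 11.415 and 11.416 refers to. Every patient has had earlier radiotherapy (3.14), and the PsP exception depends on this.

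The change is wording in 11.415, 11.416, 16.21 and 16.711, with no new tests. The price is the loss of power and the added wrongful stopping tabulated above. Section 1.3 calls pseudoprogression common after standard radiotherapy and temozolomide, so the higher end of that range cannot be ruled out. The sensitivity analysis will show whether the scoring choice changes the conclusion.

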### 1.3 Pseudoprogression can be difficult to differentiate from true tumor progression:

Following treatment with radiotherapy, inflammatory changes are often seen on MRI. Thus, strict criteria are used to categorize the nature of the tumor's response. The historical standard criteria were published by Macdonald et al. and required  $\geq 25\%$  increase in the sum of the products of perpendicular diameters of enhancing lesions, any new lesion, or clinical deterioration in order to declare progression.[11] These

criteria have come into question, as there can be significant interobserver variability, particularly in measuring irregularly shaped or cystic tumors. In addition, changes in contrast enhancement are typically nonspecific and simply represent a disrupted blood-brain barrier. Thus, fluctuations in contrast enhancement may be caused by inflammatory changes in the treated region, anti-angiogenic agents and radiation necrosis.[12] Pseudoprogression, defined as an increase in contrast enhancement that subsides without anti-neoplastic therapy, is common after standard treatment with radiotherapy and temozolomide.[13] This process is thought to be driven by radiation-induced increased permeability of the blood brain barrier. Because pseudoprogression typically occurs within 12 weeks of radiotherapy inside the high-dose region, the updated Response Assessment in Neuro-Oncology (RANO) criteria require new enhancement outside the 80% isodose line or viable tumor on histopathologic sampling for progression to be declared less than 12 weeks after radiotherapy.[14] These criteria help differentiate pseudoprogression from true progression, though challenges in interpreting changes in imaging after 12 weeks still remain.

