#### 1.5 MRI changes after bevacizumab may not accurately reflect tumor response:

While rapid responses in MRI contrast enhancement after initiation of treatment with VEGF pathway inhibitors are relatively common, it is not clear whether these changes truly reflect tumor regression or simply restoration of the blood-brain barrier.[19] Furthermore, increasing non-enhancing T2 FLAIR regions have been reported and may potentially represent tumor progression after bevacizumab.[20] This has driven

speculation that the improvement in progression-free but not overall survival with bevacizumab may be primarily driven by radiographic changes that do not fully correlate with true tumor response.

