7.6 Concurrent chemotherapy

Concurrent chemotherapy will not be required by the protocol. However, retrospective data of Mayo Clinic patients receiving reirradiation revealed a significantly lower risk of radionecrosis when bevacizumab was administered concurrently. Thus, we recommend use of concurrent bevacizumab with radiotherapy when possible.

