### 16.2 Statistical Design

#### 16.21 Decision Rules

The primary endpoint of this trial is the proportion of patients treated with F-DOPA-PET guided radiotherapy who are alive and have not progressed within 3 months. A success will be a patient who is alive and without evidence of progressive disease within 3 months from registration. Median PFS after bevacizumab failure ranges between 1-2 months.[17, 34] Thus, the largest success proportion where the proposed treatment would be considered ineffective in this population is 20%. The following Simon's Optimum design uses 20 patients to test the null hypothesis that the proportion of successes is at most 20% with an overall significance level (alpha) of 0.186, and a power of 85.9% to detect a true success proportion of 40%.

16.22 After 10 evaluable patients are accrued to this study and followed for at least 3 months, if 2 or more successes are alive and progression-free at 3 months, the results will wait until conclusion of the study. If 1 or fewer patients are alive without evidence of progression at 3 months, the study will be stopped and the treatment will be deemed ineffective in this population.

16.23 After 20 evaluable patients are accrued to this study and followed for at least 3 months, if 6 or more successes are observed we may recommend further testing of this regimen in subsequent studies in this patient population.

16.24 We will not suspend accrual between stages to allow the first 20 patients to become evaluable, unless undue toxicity is observed.

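### The operative pseudoprogression criteria omit the no-therapy condition in section 1.3, so a Preliminary PD followed by newly started or changed anti-tumour therapy can become a primary-endpoint success

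*Combined protocol and SAP*

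**What the plan says.** Section 1.3 describes pseudoprogression as "defined as an increase in contrast enhancement that subsides without anti-neoplastic therapy". Section 11.415 gives the working list, headed "Pseudoprogression (PsP): All of the following must be true". It requires that the change lies within the initial radiation volume, that no new enhancing lesion lies outside it, and that the patient is clinically stable or better. It allows the diagnosis at any time. The PsP column of 11.416 adds stable or lower steroids. Neither place mentions therapy given between scans.

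Footnote 2 of 11.416 makes confirmed PD depend on four items, one of which is being more than 3 months past radiotherapy; anything short of that is Preliminary PD. Footnote 3 back-dates PD to the Preliminary PD if it is later confirmed. If not: "If progressive disease is not confirmed the Objective Status for the current cycle can be documented as SD, PR, or CR as appropriate", and the earlier cycle may be changed to PsP.

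Section 16.21 counts as a success a patient alive and free of evident progression within 3 months of registration. The censoring rules in 16.711 cover death without progression, major treatment violation and absence of any evaluation. Neither section mentions new anti-tumour therapy or the status of a Preliminary PD.

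On bevacizumab, section 7.6 says "we recommend use of concurrent bevacizumab with radiotherapy when possible" without requiring it, and no text deals with starting it later. Of the rapid MRI changes under VEGF inhibitors, section 1.5 says "it is not clear whether these changes truly reflect tumor regression or simply restoration of the blood-brain barrier".

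**The concern.** Suppose an in-field increase at the 1-month MRI is scored Preliminary PD, the clinician then starts bevacizumab, and enhancement has fallen at the next MRI. Under section 1.3 this is not pseudoprogression, because the change did not subside untreated. Under 11.415, 11.416 and footnote 3 it can be called pseudoprogression, with the current cycle scored SD, PR or CR.

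Therapy given because of apparent progression would then supply the evidence that cancels it, and the effect of that therapy would be credited to PET-guided reirradiation. This route can only turn failures into successes. The trial has one arm and a fixed threshold of 6 successes in 20, so no control group would absorb the error, and each relabelled patient moves the observed rate by 1/20 = 5 percentage points.

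**Working it through.** **1. The texts side by side**

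| Place | Condition on therapy between scans |
|---|---|
| 1.3 (Background) | Must subside without anti-neoplastic therapy |
| 11.415 | None |
| 11.416, PsP column | None (steroids only) |
| 11.416, footnote 3 | None |
| 16.21, success | None |
| 16.711, censoring | None |

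**2. Timing**

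Ten weekday fractions take about 12 days. If radiotherapy began on the day of registration, the 3-month post-RT MRI would fall at about day 12 + 91 = 103, or day 89 at the early edge of its 14-day window. The 1-month MRI is therefore usually the only scheduled post-RT scan within 3 months of registration. Progression in that period is at first Preliminary PD, because confirmation needs more than 3 months after radiotherapy. Whether it counts depends on a later scan, which leaves time for new therapy in between.

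**3. The plan's own figures**

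Inputs from 16.21 to 16.23: stop if 1 or fewer successes in 10; positive if 6 or more in 20. The stated operating characteristics are "with an overall significance level (alpha) of 0.186, and a power of 85.9% to detect a true success proportion of 40" per cent, with a null of 20%.

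P(positive | p) = Σ over x = 2 to 10 of P[Bin(10, p) = x] × P[Bin(10, p) ≥ max(0, 6 − x)]

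- p = 0.20: 0.1863 (stated 0.186)
- p = 0.40: 0.8586 (stated 85.9%)

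Both agree. A single-stage rule of 6 in 20 gives 0.1958 and 0.8744, so the stated figures are those of the two-stage rule. The design arithmetic is not in question.

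**4. Sensitivity to relabelling**

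Let m be the share of true failures relabelled PsP after new therapy and counted as successes. The documents give no value for m, so it is an assumption, shown from zero. At a true rate of 20%:

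p_eff = 0.20 + 0.80 m; expected relabelled patients among 20 = 16 m

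| m | p_eff | Expected patients | P(positive) |
|---|---|---|---|
| 0 | 0.200 | 0 | 0.186 |
| 1% | 0.208 | 0.16 | 0.212 |
| 1.5% | 0.212 | 0.24 | 0.226 |
| 3% | 0.224 | 0.48 | 0.268 |
| 5% | 0.240 | 0.80 | 0.328 |
| 8.75% | 0.270 | 1.40 | 0.447 |

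m can be read as (share of failures who start new therapy after an in-field Preliminary PD) × (share of those whose scan then improves enough). For example, 10% × 10% = 1%, 5% × 30% = 1.5%, 10% × 30% = 3% and 25% × 35% = 8.75%. The 30 to 35% is the bevacizumab response range quoted in section 1.4. The other shares are assumptions.

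**The case against.** Several points on the other side stand.

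- **The wording is permissive.** Footnote 3 says what can be documented, and the plan never says how an unresolved Preliminary PD counts at 3 months. A reader might infer that treated progressions necessarily become successes. The documents support only that they can.
- **Section 1.3 excludes the case.** A reader might infer that the protocol sanctions erasing treated progressions. It does not: its Background definition and its operative list disagree. But 11.415 is the list that is applied, and it omits the condition.
- **Other safeguards exist.** SD, PR and CR need T2/FLAIR that is stable (or, for PR and CR, improved), no new lesion, acceptable steroid dose and clinical stability. SD needs at least 4 weeks; PR and CR must be sustained and confirmed. Section 1.5 reports growing T2/FLAIR regions after bevacizumab, so some treated patients would fail these conditions. MRIs are also read centrally, and later confirmed PD is back-dated. All of this narrows the gap, but none of it excludes a drug-induced fall in enhancement.
- **The size is uncertain.** A reader might take 27 to 45% as the false-positive rate. That range assumes 10 to 25% of failures start bevacizumab, which has no source in the documents, and it omits lower values. The 30 to 35% response comes from bevacizumab trials in recurrent glioblastoma, whereas the 20% null rests on outcomes after bevacizumab failure, and section 1.7 says many patients are on bevacizumab or recently were. Deaths, clinical decline and out-of-field lesions cannot take this route.
- **Counting new therapy as failure is a choice of estimand.** The documents do not show whether the historical controls were scored that way.

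**Conclusion.** The concern holds as an unreconciled conflict between section 1.3 and the operative criteria. It lets a Preliminary PD followed by newly started or changed anti-tumour therapy become a primary-endpoint success, and the resulting bias can run only toward success. Patients on unchanged bevacizumab since radiotherapy are not affected.

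The size cannot be estimated from the documents. The design is nevertheless sensitive: at a true rate of 20%, relabelling 5% of failures (less than one patient expected among 20) raises the chance of a positive result from 0.186 to 0.328. This rests on the assumed m, on independent binomial outcomes, and on relabelled patients being counted as successes. That last step is an inference, since back-dating applies only to confirmed PD and 16.21 is silent. The change should be made, because in a single-arm trial this should not be left to case-by-case judgement.

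**What to change.** The change concerns endpoint classification only, not how patients are treated.

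1. In 11.415, the PsP column of 11.416 and footnote 3, add: no new or changed anti-tumour therapy (including starting or restarting bevacizumab) and no tumour resection between the Preliminary PD scan and the scan used to resolve it. Unchanged ongoing bevacizumab does not count as new.
2. In footnote 3 and 16.21, state that a Preliminary PD followed by such therapy or resection before it is resolved is not a success and is dated at the Preliminary PD, unless pathology recorded under 7.10 shows treatment effect without tumour.
3. Report the as-written scoring as a sensitivity analysis.
4. Make sure the Concomitant Medications form captures therapy start dates. A reader might infer that it already does, but section 4.0 asks only for current medications and the form's fields are not shown. Section 12.0 mentions dates for salvage chemotherapy only as a descriptive factor.

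The cost is protocol wording and possibly one form field. The downside is that some true pseudoprogressions, or radionecrosis treated early, would count as failures, so the reported success rate may be lower, by an amount the documents do not allow us to compute. The sensitivity analysis keeps both scorings visible.
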